8.2 Populations for Analyses

For the purposes of analysis, the following analysis sets are defined:

Population	Description
Enrolled	All participants who signed the ICF (including screening failures).
Modified Intent to Treat (mITT) Population	The mITT Population comprises all participants who take at least 1 dose of any of the study treatments, and have at least 1 measurement on the primary endpoint.
Safety Population	The Safety Population consists of all participants who receive at least 1 dose of any of the study treatments. Participants will be analyzed for safety based on the treatment received.
Per Protocol (PP) Population	The PP Population consists of all participants without any major protocol violations that could influence efficacy assessment. Participants in this population will be analyzed according to the treatment they actually received.

8.3 Interim Analyses

No interim analysis is planned.

9 Supporting Documentation and Operational Considerations

9.1 Appendix 1: Regulatory, Ethical, and Study Oversight Considerations

9.1.1 Regulatory and Ethical Considerations

- This study will be conducted in accordance with the protocol and with:
 - Consensus ethical principles derived from international guidelines including the Declaration of Helsinki and Council for International Organizations of Medical Sciences International Ethical Guidelines.
 - Applicable International Conference on Harmonisation (ICH) Good Clinical Practice (GCP) Guidelines.
 - Applicable laws and regulations.
- The protocol, protocol amendments, ICF, and other relevant documents (e.g., advertisements) must be submitted to an IRB/IEC by the Investigator and reviewed and approved by the IRB/IEC before the study is initiated.
- Any amendments to the protocol will require IEC/IRB approval before implementation of changes made to the study design, except for changes necessary to eliminate an immediate hazard to study participants.
- The Investigator will be responsible for the following:
 - Providing written summaries of the status of the study to the IRB/IEC annually or more frequently in accordance with the requirements, policies, and procedures established by the IRB/IEC.
 - Notifying the IRB/IEC of SAE or other significant safety findings as required by IRB/IEC procedures.
 - Overall conduct of the study at the site and adherence to requirements of 21 Code of Federal Regulations (CFR), ICH GCP guidelines, the IRB/IEC guidelines, European regulation 536/2014 for clinical studies (if applicable), and all other applicable local regulations.

9.1.2 Financial Disclosure

Investigators and sub-Investigators will provide the Sponsor with sufficient, accurate financial information in accordance with local regulations to allow the Sponsor to submit complete and accurate financial certification or disclosure statements to the appropriate regulatory authorities. Investigators are responsible for providing information on financial interests during the course of the study and for 1 year after completion of the study.

9.1.3 Informed Consent Process

- The Investigator or his/her representative will explain the nature of the study to the participant or his/her legally authorized representative and answer all questions regarding the study.
- Participants must be informed that their participation is voluntary. Participants will be required to sign a statement of informed consent that meets the requirements of 21 CFR 50, local regulations, ICH guidelines, Health Insurance Portability and Accountability Act requirements, where applicable, and the IRB/IEC or study center.
- The medical record must include a statement that written informed consent was obtained before the participant was enrolled in the study and the date the written consent was obtained. The authorized person obtaining the informed consent must also sign the ICF.
- Participants must be re-consented to the most current version of the ICF(s) during their participation in the study.
- A copy of the signed ICF(s) must be provided to the participant or the participant's legally authorized representative.

If a protocol amendment is required, the ICF may need to be revised to reflect the changes to the protocol. If the ICF is revised, it must be reviewed and approved by the appropriate IEC/IRB, and signed by all participants subsequently enrolled in the study as well as those currently enrolled in the study.

9.1.4 Data Protection

- Participants will be assigned a unique identifier by the Sponsor. Any participant records or datasets that are transferred to the Sponsor will contain the identifier only; participant names or any information which would make the participant identifiable will not be transferred.
- The participant must be informed that his/her personal study-related data will be used by the Sponsor in accordance with local data protection law. The level of disclosure must also be explained to the participant.
- The participant must be informed that his/her medical records may be examined by Clinical Quality Assurance auditors or other authorized personnel appointed by the Sponsor, by appropriate IRB/IEC members, and by inspectors from regulatory authorities.

9.1.5 Data Quality Assurance

- All participant data relating to the study will be recorded on printed or eCRFs unless transmitted to the Sponsor or designee electronically (e.g., laboratory data). The Investigator is responsible for verifying that data entries are accurate and correct by physically or electronically signing the eCRF.
- The Investigator must maintain accurate documentation (source data) that supports the information entered in the eCRF.
- The Investigator must permit study-related monitoring, audits, IRB/IEC review, and regulatory agency inspections and provide direct access to source data documents.
- The Sponsor or designee is responsible for the data management of this study including quality checking of the data.
- Records and documents, including signed ICF, pertaining to the conduct of this study must be retained by the Investigator for 5 years after study completion unless local regulations or institutional policies require a longer retention period. No records may be destroyed during the retention period without the written approval of the Sponsor. No records may be transferred to another location or party without written notification to the Sponsor.
- All data generated by the site personnel will be recorded electronically at each study center using eCRFs. Data from external sources (such as laboratory data) will be entered into the database. Corrections to the data fields will be captured in an audit trail. The reason for change, the name of the person who performed the change, together with the time and date will be logged to provide an audit trail.

9.1.6 Source Documents

- Source documents provide evidence for the existence of the participant and substantiate the integrity of the data collected. Source documents are filed at the Investigator's site.
- Data entered in the eCRF that are transcribed from source documents must be consistent with the source documents or the discrepancies must be explained. The Investigator may need to request previous medical records or transfer records, depending on the study. Also, current medical records must be available.

9.1.7 Study and Site Closure

The Sponsor designee reserves the right to close the study site or terminate the study at any time for any reason at the sole discretion of the Sponsor. Study sites will be closed upon study

completion. A study site is considered closed when all required documents and study supplies have been collected and a study site closure visit has been performed.

The Investigator may initiate study site closure at any time, provided there is reasonable cause and sufficient notice is given in advance of the intended termination.

Reasons for the early closure of a study site by the Sponsor or Investigator may include but are not limited to:

- Failure of the Investigator to comply with the protocol, the requirements of the IRB/IEC or local health authorities, the Sponsor's procedures, or GCP guidelines.
- Inadequate recruitment of participants by the Investigator.
- Discontinuation of further study treatment development.

9.1.8 Publication Policy

- Authorship will be determined by mutual agreement and in line with International Committee of Medical Journal Editors authorship requirements.
- The Sponsor retains the right to disapprove any submission for publication, including any publication using trial data, including abstracts, presentations or manuscripts.
- A summary of the study results will also be posted in a publicly accessible database (e.g., www.ClinTrials.gov).

9.1.9 Protocol Approval and Amendment

Before the start of the study, the study protocol and/or other relevant documents will be approved by the IEC/IRB/Competent Authorities, in accordance with local legal requirements. The Sponsor must ensure that all ethical and legal requirements have been met before the first participant is enrolled in the study.

This protocol is to be followed exactly. To alter the protocol, amendments or exceptions must be written, receive approval from the appropriate personnel, and receive IRB/IEC/Competent Authority approval prior to implementation (if appropriate).

Administrative changes (not affecting the participant benefit/risk ratio) may be made without the need for a formal amendment. All amendments will be distributed to all protocol recipients, with appropriate instructions.

9.1.10 Liability and Insurance

The Sponsor will take out reasonable third-party liability insurance cover in accordance with all local legal requirements. The civil liability of the Investigator, the persons instructed by him or her and the hospital, practice, or institute in which they are employed and the liability of the Sponsor with respect to financial loss due to personal injury and other damage that may arise as a result of the carrying out of this study are governed by the applicable law.

The Sponsor will arrange for participants participating in this study to be insured against financial loss due to personal injury caused by the pharmaceutical products being tested or by medical steps taken in the course of the study.

9.1.10.1 Access to Source Data

Regulatory authorities of certain countries, IRBs, IECs, and/or the Sponsor may wish to carry out source data checks and/or on-site audit inspections. Direct access to source data will be required for these inspections and audits; they will be carried out giving due consideration to data protection and medical confidentiality. The Investigator assures the Sponsor of the necessary support at all times.

9.2 Appendix 2: Clinical Laboratory Tests

- The tests detailed in Table 2 will be performed by local laboratory.
- Laboratory testing is performed non-fasting.
- Additional tests may be performed at any time during the study as determined necessary by the Investigator or required by local regulations.

Table 2: Protocol-Required Safety Laboratory Assessments

Laboratory Assessments	Parameters		
Hematology	Hematocrit Hemoglobin Platelet Count RBC Count	RBC Indices	WBC count with Differential

Serum Chemistry	Albumin	ALT
	BUN	AST
	Creatinine	Alkaline phosphatase
	Potassium	Calcium
	Sodium	Glucose
	Bilirubin	Total cholesterol
	Total Protein	Chloride
	Uric acid	Bicarbonate
Other Tests	
• Urinalysis• HbA1c (Screening Visit only)• Serum hCG pregnancy test at screening. Additional testing may be performed if needed in WOCBP.• Urine test of drugs of abuse (marijuana, cocaine, amphetamine, methamphetamine, opiates, phencyclidine)	

Abbreviations: ALT = alanine aminotransferase; AST = aspartate aminotransferase; BUN = blood urea nitrogen; HbA1c = hemoglobin A1c (glycated hemoglobin); hCG = human chorionic gonadotropin; RBC = red blood cell count; WBC= white blood cell; WOCBP = women of childbearing potential.

Investigators must document their review of each laboratory safety report.

9.3 Appendix 3: Adverse Events: Definitions and Procedures for Recording, Evaluating, Follow-up, and Reporting

Definition of AE

AE Definition

• An AE is any untoward medical occurrence in a participant or clinical study participant, temporally associated with the use of a study treatment, whether or not considered related to the medicinal product.• NOTE: An AE can therefore be any unfavorable and unintended sign (including an abnormal laboratory finding), symptom, or disease (new or exacerbated) temporally associated with the use of a study treatment.

Events Meeting the AE Definition

• Any abnormal laboratory test results (hematology, clinical chemistry, or urinalysis) or other safety assessments (e.g., ECG, radiological scans, vital signs measurements), including those that worsen from baseline, considered clinically significant in the medical and scientific judgment of the Investigator (i.e., not related to progression of underlying disease).

- Exacerbation of a chronic or intermittent pre-existing condition including either an increase in frequency and/or intensity of the condition.
- New conditions detected or diagnosed after study treatment administration even though it may have been present before the start of the study.
- Signs, symptoms, or the clinical sequelae of a suspected drug-drug interaction.
- Signs, symptoms, or the clinical sequelae of a suspected overdose of either study treatment or a concomitant medication. Overdose per se will not be reported as an AE/SAE unless it is an intentional overdose taken with possible suicidal/self-harming intent. Such overdoses should be reported regardless of sequelae.
- "Lack of efficacy" or "failure of expected pharmacological action" per se will not be reported as an AE or SAE. Such instances will be captured in the efficacy assessments. However, the signs, symptoms, and/or clinical sequelae resulting from lack of efficacy will be reported as an AE or SAE if they fulfill the definition of an AE or SAE.

Events NOT Meeting the AE Definition

- Any clinically significant abnormal laboratory findings or other abnormal safety assessments which are associated with the underlying disease, unless judged by the Investigator to be more severe than expected for the participant's condition.
- The disease/disorder being studied or expected progression, signs, or symptoms of the disease/disorder being studied, unless more severe than expected for the participant's condition.
- Medical or surgical procedure (e.g., endoscopy, appendectomy): the condition that leads to the procedure is the AE.
- Situations in which an untoward medical occurrence did not occur (social and/or convenience admission to a hospital).
- Anticipated day-to-day fluctuations of pre-existing disease(s) or condition(s) present or detected at the start of the study that do not worsen.

Definition of SAE

If an event is not an AE per definition above, then it cannot be an SAE even if serious conditions are met (e.g., hospitalization for signs/symptoms of the disease under study, death due to progression of disease).

An SAE is defined as any untoward medical occurrence that, at any dose:

Results in death

Is life-threatening

The term 'life-threatening' in the definition of 'serious' refers to an event in which the participant was at risk of death at the time of the event. It does not refer to an event, which hypothetically might have caused death, if it were more severe.

Requires inpatient hospitalization or prolongation of existing hospitalization

In general, hospitalization signifies that the participant has been detained (usually involving at least an overnight stay) at the hospital or emergency ward for observation and/or treatment that would not have been appropriate in the physician's office or outpatient setting. Complications that occur during hospitalization are AE. If a complication prolongs hospitalization or fulfills any other serious criteria, the event is serious. When in doubt as to whether "hospitalization" occurred or was necessary, the AE should be considered serious.

Hospitalization for elective treatment of a pre-existing condition that did not worsen from baseline is not considered an AE.

Results in persistent disability/incapacity

- The term disability means a substantial disruption of a person's ability to conduct normal life functions.
- This definition is not intended to include experiences of relatively minor medical significance such as uncomplicated headache, nausea, vomiting, diarrhea, influenza, and accidental trauma (e.g., sprained ankle) which may interfere with or prevent everyday life functions but do not constitute a substantial disruption.

Is a congenital anomaly/birth defect

Other situations

- Medical or scientific judgment should be exercised in deciding whether SAE reporting is appropriate in other situations such as important medical events that may not be immediately life-threatening or result in death or hospitalization but may jeopardize the participant or may require medical or surgical treatment to prevent one of the other outcomes listed in the above definition. These events should usually be considered serious.

Examples of such events include invasive or malignant cancers, intensive treatment in an emergency room or at home for allergic bronchospasm, blood dyscrasias, or convulsions that do not result in hospitalization, or development of drug dependency or drug abuse.

Recording and Follow-up of AE and SAE

AE and SAE Recording

- When an AE/SAE occurs, it is the responsibility of the Investigator to review all documentation (e.g., hospital progress notes, laboratory, and diagnostics reports) related to the event.
- The Investigator will then record all relevant AE/SAE information in the eCRF.
- It is **not** acceptable for the Investigator to send photocopies of the participant's medical records in lieu of completion of the AE/SAE eCRF page.
- There may be instances when copies of medical records for certain cases are requested by the Sponsor. In this case, all participant identifiers, with the exception of the participant number, will be blinded on the copies of the medical records before submission to the Sponsor.
- The Investigator will attempt to establish a diagnosis of the event based on signs, symptoms, and/or other clinical information. In such cases, the diagnosis (not the individual signs/symptoms) will be documented as the AE/SAE.

Assessment of Intensity

The Investigator will make an assessment of intensity for each AE and SAE reported during the study and assign it to one of the following categories:

- Mild: An event that is easily tolerated by the participant, causing minimal discomfort and not interfering with everyday activities.
- Moderate: An event that causes sufficient discomfort and interferes with normal everyday activities.
- Severe: An event that prevents normal everyday activities. An AE that is assessed as severe should not be confused with an SAE. Severe is a category utilized for rating the intensity of an event; and both AE and SAE can be assessed as severe.

An event is defined as 'serious' when it meets at least one of the predefined outcomes as described in the definition of an SAE, NOT when it is rated as severe.

Assessment of Causality

- The Investigator is obligated to assess the relationship between study treatment and each occurrence of each AE/SAE.
- A "reasonable possibility" of a relationship conveys that there are facts, evidence, and/or arguments to suggest a causal relationship, rather than a relationship cannot be ruled out.
- The Investigator will use clinical judgment to determine the relationship.
- Alternative causes, such as underlying disease(s), concomitant therapy, and other risk factors, as well as the temporal relationship of the event to study treatment administration will be considered and investigated.
- The Investigator will also consult the Investigator's Brochure and/or Product Information, for marketed products, in his/her assessment.
- For each AE/SAE, the Investigator **must** document in the medical notes that he/she has reviewed the AE/SAE and has provided an assessment of causality.
- There may be situations in which an SAE has occurred and the Investigator has minimal information to include in the initial report to the Sponsor. However, **it is very important that the Investigator always make an assessment of causality for every event before the initial transmission of the SAE data to the Sponsor.**
- The Investigator may change his/her opinion of causality in light of follow-up information and send an SAE follow-up report with the updated causality assessment.
- The causality assessment is one of the criteria used when determining regulatory reporting requirements.

Follow-up of AE and SAE

- The Investigator is obligated to perform or arrange for the conduct of supplemental measurements and/or evaluations as medically indicated or as requested by the Sponsor to elucidate the nature and/or causality of the AE or SAE as fully as possible. This may include additional laboratory tests or investigations, histopathological examinations, or consultation with other health care professionals.
- If a participant dies during participation in the study, the Investigator will provide the Sponsor with a copy of any post-mortem findings including histopathology.

- New or updated information will be recorded in the originally completed eCRF.
- The Investigator will submit any updated SAE data to the Sponsor within 24 hours of receipt of the information.

Reporting of SAE to Sponsor

SAE Reporting to Sponsor

- The Investigator must report any SAEs to the Sponsor within 24 hours of becoming aware of the event.
- When calling to report an SAE, state that you are reporting an SAE and give the Investigator's name, your name, the telephone number where you can be reached, and the protocol number and title.
- The Investigator and the Sponsor will review each SAE report and the Sponsor will evaluate the seriousness and the causal relationship of the event to study treatment. In addition, the Sponsor will evaluate the expectedness according to the reference documents (Investigator's Brochure or US product labeling for atomoxetine or dronabinol). Based on the Investigator and Sponsor's assessment of the event, a decision will be made concerning the need for further action.
- After the study is completed at a given site, the electronic data collection tool will be taken off-line to prevent the entry of new data or changes to existing data.
- If a site receives a report of a new SAE from a study participant or receives updated data on a previously reported SAE after the electronic data collection tool has been taken off-line, then the site can report this information on a paper SAE form or by telephone.

All SAEs will be recorded from signing of informed consent until the end of the study. Serious adverse events occurring after the end of the study and coming to the attention of the Investigator must be reported only if they are considered (in the opinion of the Investigator) causally-related to study treatment.

Suspected Unexpected Serious Adverse Reactions (SUSARs)

Any AE that is serious, associated with the use of the study treatment, and unexpected (SUSAR) has additional reporting requirements, as described below.

- If the SUSAR is fatal or life-threatening, associated with study treatment, and unexpected, regulatory authorities and IECs will be notified within 7 calendar days after the Sponsor learns of the event. Additional follow-up (cause of death, autopsy report, and hospital report) information should be reported within an additional 8 days (15 days total).
- If the SUSAR is not fatal or life-threatening but is otherwise serious, associated with study treatment, and unexpected, regulatory authorities and IECs will be notified within 15 calendar days after the Sponsor learns of the event.

The Sponsor will notify the Investigators in a timely fashion of relevant information about SUSARs that could adversely affect the safety of participants. Follow-up information may be submitted if necessary.

The Sponsor will also provide annual safety updates to the regulatory authorities and IECs responsible for the study. These updates will include information on SUSARs and other relevant safety findings.

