4.1 Overall Design

The SEED study is an open-label, 4 consecutive period dose-escalation study of combinations of atomoxetine and dronabinol in participants with moderate to severe OSA. Participants will undergo initial pre-screening to determine potential study eligibility. Participants selected for further screening should either have a previous history of OSA of a severity consistent with enrollment criteria or be at high risk (e.g. as assessed by STOP-Bang Questionnaire score). Only participants who meet all non-PSG enrollment criteria at Visit 1 are eligible for a screening PSG. On a case by case basis and with agreement of the Sponsor a PSG conducted at the site within 3 months may be used instead of the Screening PSG.

Participants who meet all enrollment criteria will receive an escalating dose of atomoxetine the first week: 3 days of atomoxetine 40 mg followed by 4 days of atomoxetine 80 mg. Participants will then receive escalating dose combinations of atomoxetine and dronabinol for the next 3 weeks. The weekly dose schedule is as follows:

- Week 1: atomoxetine 40 mg x 3 days, then 80 mg x 4 days
- Week 2: atomoxetine 40 mg/dronabinol 2.5 mg
- Week 3: atomoxetine 80 mg/dronabinol 5 mg
- Week 4: atomoxetine 80 mg/dronabinol 10 mg

Dose escalation will be based on safety and tolerability, as assessed at weekly clinic visits and by telephone contact with participants mid-week of each at-home dosing period. Patients who do not tolerate dose escalation will discontinue dosing.

Three on-drug PSGs will be conducted on the final night of the following dosing periods:

- 1st week, dosing atomoxetine 80 mg alone
- 3rd week, dosing atomoxetine 80 mg/dronabinol 5 mg
- 4th week, dosing atomoxetine 80 mg/dronabinol 10 mg

Study drug for Week 1 is dispensed to participants at Visit 2.. Any unused Week 1 study drug is returned at Visit 3. Similarly, study drug for Week 2, 3, and 4 is dispensed at Visits 3, 4 and 5, and unused study drug similarly returned at the subsequent visit.

Dosing of the study treatment will occur each night at the participant's usual bedtime, both during at-home nights and Visit 3, Visit 5 and Visit 6 PSG nights. Study drug dose on PSG nights

[figure not shown]
is from the supply dispensed to the participant if available, but can be provided from separate site supply.

The morning of each PSG the PGI-S, PROMIS assessments, DSST, VOLT and PVT will be administered.

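### The plan does not say how an adverse event that worsens at a later dose is dated or assigned to a dose, so worsening on the combination may be placed at an earlier dose or lost

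*Combined protocol and SAP*

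**What the plan says.** Section 4.1 describes an "open-label, 4 consecutive period dose-escalation study of combinations of atomoxetine and dronabinol". Everyone follows the same order: atomoxetine 40 mg then 80 mg in Week 1, then 40/2.5, 80/5 and 80/10 in Weeks 2 to 4. The synopsis names atomoxetine alone as a comparator, and adverse events are listed among the safety endpoints in Section 3.

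Four pieces of text govern how a change in an adverse event reaches the data:

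- Section 9.3, under its heading on intensity, states: "The Investigator will make an assessment of intensity for each AE and SAE reported during the study". Each event then goes into a single category: mild, moderate or severe. The section does not say whether this is intensity at onset or at its maximum, and it asks for no date of change.
- Section 9.3, Follow-up of AE and SAE: "New or updated information will be recorded in the originally completed eCRF". The heading covers non-serious events too.
- Section 9.3, Events Meeting the AE Definition: the item on worsening reads "Exacerbation of a chronic or intermittent pre-existing condition including either an increase in frequency and/or intensity of the condition". It addresses conditions present before the study, not an event that began on study drug.
- Section 8.2, Safety Population: "Participants will be analyzed for safety based on the treatment received".

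The rest of Section 8 covers sample size and interim analyses. It contains no adverse event tabulation and no rule for assigning an event to one of the doses a participant takes in turn.

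**The concern.** A participant who finishes dosing has received every regimen, so analysing by treatment received does not settle where an event belongs. Suppose an event begins in Week 1 on atomoxetine, continues, and becomes more intense once dronabinol is added or raised. That worsening bears directly on the comparison with atomoxetine alone. If the existing record is updated in place, the higher grade can carry the Week 1 onset date. If it is not updated, the higher grade is never recorded. In neither case does the combination dose show the worsening.

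The same thing can happen between combination doses, where worsening at a higher dronabinol dose may be shown at a lower one. With no concurrent control, the contrast between periods within participants is the only source of dose information on adverse events.

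**Working it through.** The plan gives no figure on this point to reproduce. The check compares recording conventions and then sizes one event.

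**Step 1: possible cases.** Take the four weekly periods in 4.1: Week 1 (atomoxetine alone), 40/2.5, 80/5 and 80/10. An event that starts in one period and worsens in a later one can do so in 4 × 3 / 2 = 6 ways. Three start in Week 1 (worsening at 40/2.5, 80/5 or 80/10). Three start on a combination (40/2.5 to 80/5, 40/2.5 to 80/10, 80/5 to 80/10).

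**Step 2: what each convention shows,** with one onset date per record and tabulation by dose at onset (both assumed):

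| Recording convention | Worsening shown at the dose where it occurred | What appears instead |
|---|---|---|
| First grade kept | 0 of 6 | Higher grade appears at no dose |
| Grade overwritten, onset date kept | 0 of 6 | Higher grade appears at the earlier dose |
| Increase in intensity recorded with its own date | 6 of 6 | – |

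Under overwriting, the three Week 1 cases move a worsening from the combination to atomoxetine alone. The other three move it from a higher to a lower dronabinol dose.

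**Step 3: which convention the text favours.** The follow-up instruction points to the existing record. The intensity text speaks of each event. The causality text is finer: "The Investigator is obligated to assess the relationship between study treatment and each occurrence of each AE/SAE". No equivalent wording applies to intensity. The text therefore leans towards the first two rows of the table but does not fix either one.

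**Step 4: size of one event.** Inputs from 8.1 are 15 enrolled and 12 assumed to complete. If exactly 12 complete, between 12 and 15 participants receive 80/10.

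- All 15 reach the dose: 1/15 = 6.7 percentage points.
- 12 at 80/10: 1/12 = 8.3 percentage points.
- One Week 1 event worsening at 80/10 and overwritten: Week 1 gains 1/15 and 80/10 loses 1/12, so the contrast between them shifts by 6.7 + 8.3 = 15.0 points. With 15 in both periods it shifts by 6.7 + 6.7, or 2/15 = 13.3 points.
- One such event with the first grade kept: only 80/10 changes, losing 6.7 to 8.3 points.

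The documents give no basis for the number of such events, so these are per-event figures only.

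**The case against.** A reader might infer that such worsening is bound to appear at the wrong dose or nowhere. The documents do not support that. The consequence needs a single grade, a single date and tabulation by dose at onset. The protocol states none of these. The eCRF, its completion instructions or a separate analysis plan could hold dated intensity changes. The follow-up sentence also sits beside items on supplemental tests and post-mortem findings, and it says where information is filed, not that a grade is overwritten. This stands, and it limits the point to a risk.

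The general definition in Appendix 3 includes a "symptom, or disease (new or exacerbated) temporally associated with the use of a study treatment". An investigator may therefore report a worsening as a new event. That is true, but nothing requires it, and no recording rule follows from it, so practice may vary from one event to the next.

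A reader might also infer that the dose at worsening could never be recovered. That goes too far. Section 9.1.5 provides an audit trail with the date of each correction, and with weekly visits and mid-week calls this may help locate the period. But it dates the data edit, not the symptom, and it is not an analysis variable. If the grade is never updated, there is no edit to trace.

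Other safety information is still tied to dose. Participants who do not tolerate escalation stop dosing (4.1), withdrawal because of an adverse event is a recorded reason (6.6), and vital signs, DSST, VOLT and PVT are collected by visit. It would therefore be wrong to say that the combination doses would show nothing.

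Finally, not every participant reaches every dose, and the escalation is strictly upward only for dronabinol (0, 2.5, 5, 10 mg). Atomoxetine runs 40, 80, 40, 80, 80 mg, so a later period does not always mean more of both drugs.

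**Conclusion.** The point holds as a gap in recording and attribution. The plan gives each event one intensity category, directs updates to the existing record, dates no change, and does not assign an event to a dose when a participant takes several in sequence. Worsening in a later period may therefore be misplaced or lost, and for events that begin on atomoxetine alone the error favours the combination.

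The affected class is narrow: events that start in one period, persist and worsen in a later one. The per-event size in the working assumes that each event is in a different participant and that the data are tabulated by dose at onset; the total effect cannot be estimated. This is more than missing detail, because a date of worsening that was never collected cannot be reliably rebuilt at analysis, and comparison with atomoxetine alone is a stated aim. It should be changed, as a cheap improvement.

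**What to change.** In Appendix 3, require each increase in intensity of an ongoing adverse event to be captured with its own date, intensity and causality. A linked new record or a dated intensity change within the same record would both serve; choose one and put it in the eCRF instructions before data collection.

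In a new safety-analysis subsection of Section 8, or in the SAP (8.2 only defines populations and is the wrong place):

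- tabulate events by the dose in effect at onset or at worsening;
- show, for each dosing period, the participants with the event new or ongoing at its worst intensity in that period, with the number dosed in that period as denominator.

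The cost is a few more adverse event entries and one extra table. If linked records are used, the link must be applied so that a participant is counted once per event within a period.
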